 - ALT $>2\times$ ULN and bilirubin $>1.5\times$ ULN (isolated bilirubin $>1.5\times$ ULN is acceptable if bilirubin is fractionated and direct bilirubin $<35\%$).
 - Haematology – Haemoglobin <10.0 g/dL at screening
 - Prostate Specific Antigen (PSA) >4.0 ng/mL
13. Presence of hepatitis B surface antigen (HBsAg), positive hepatitis C antibody test result at screening or within 3 months prior to first dose of study treatment. NOTE: Participants with positive Hepatitis C antibody due to prior resolved disease can be enrolled, only if a confirmatory negative Hepatitis C RNA PCR test is obtained.
14. QT interval corrected for heart rate by Bazett's formula (QTcB) or QT interval corrected for heart rate by Fridericia's formula (QTcF) >450 msec or QT interval corrected for heart rate (QTc) >480 msec in participants with Bundle Branch Block based on a single ECG.
15. A positive test for HIV antibody.

Other Exclusions

16. More than two moderate/severe COPD exacerbations within the past year
 - Exacerbation is defined as worsening of two or more of the following major symptoms: dyspnoea, sputum volume, sputum purulence OR worsening of any one major symptom together with at least one of the following additional symptoms: sore throat, colds (nasal discharge and/or nasal congestion), fever $> 37.5^{\circ}\text{C}$ without any explained cause, increased cough, increased wheeze.
 - A moderate exacerbation is defined as an exacerbation that requires treatment with antibiotics and/or oral steroids. A severe exacerbation is defined as an event that is additionally associated with hospitalization or emergency room visit.
17. Any moderate/severe COPD exacerbation in the 4 weeks preceding the screening visit.
18. Participants on long term oxygen therapy (LTOT), defined as prescribed continuous oxygen use for >14 hours/day.
19. Clinically diagnosed history of drug or alcohol abuse within 5 years prior to randomization.
20. History of sensitivity to any of the study medications, or components thereof or a history of drug or other allergy that, in the opinion of the investigator or GSK Medical Monitor, contraindicates their participation.
21. Participation in a formal pulmonary rehabilitation exercise program outside or inside the home, either currently or completed within the previous 6 months.

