8.1.2. QTc Stopping Criteria

For trial eligibility and discontinuation, ideally the same QT correction formula will be used for *all* participants within a single trial. However, GSK does recognize that because multiple sites from different countries may participate in a single trial, this may not always be possible since QT correction formulae pre-programmed by different manufacturers within ECG machines tend to vary. In these situations, the same QT correction formula must be used throughout the trial for an individual participant.

- The QTc should be based on averaged QTc values of triplicate ECGs obtained over a brief (e.g., 5-10 minute) recording period.

A participant who meets either of the bulleted criteria below will be withdrawn from the study:

- QTc >500 msec OR Uncorrected QT >600 msec
- Increase from baseline of QTc >60 msec

For participants with underlying **bundle branch block**, follow the discontinuation criteria listed below:

Baseline QTc with Bundle Branch Block	Discontinuation QTc with Bundle Branch Block
<450 msec	>500 msec
450 – 480 msec	≥530 msec

See the SoA for data to be collected at the time of treatment discontinuation and follow-up and for any further evaluations that need to be completed.

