## 12. APPENDICES

### 12.1. Appendix 1: Protocol Deviation Management and Definitions for Per Protocol Population

#### 12.1.1. Exclusions from Per Protocol Population

The criteria for subject exclusion from the Per Protocol population are based on 'the Protocol Deviation Specification-version 2.0-31August 2018'. Refer to the latest version of the rules document prior to finalisation of the per protocol population.

The following criteria define the protocol deviations Potential protocol deviations leading to exclusion from PP population will be reviewed by the study team to confirm that they meet these criteria. This review will occur before the clinical database has been frozen for analysis. Note: None of the protocol deviations need the data unblinding to take the decision whether the subject data to be excluded from analysis or not. So, the protocol deviation meeting post unblinding won't be conducted.

A subject meeting any of the following criteria will be excluded from the Per Protocol population:

Number	Exclusion Description
01	Inclusion #1 – Subject not 50-75 years of age inclusive
02	Inclusion #3 – Did not have Confirmed Diagnosis of COPD
03	Inclusion #4 – SPPB: Score of "0" on any component of the SPPB or Timed Chair Stand Score is < 1 and > 3
04	Inclusion #5 – BMI not within 18-32 kg/m  (inclusive)
05	Inclusion #6 – not current smokers or former smokers with a cigarette smoking history of <10 pack years
06	Exclusion #1-7 – Prohibited Medical Conditions
07	Exclusion #8-10 – Prohibited Treatments
08	Exclusion #11 – Prohibited Prior/Current Clinical Study Experience
09	Exclusion #12-13 – Key laboratory tests out of range
10	Exclusion #14 – ECG values above ranges (QTc > 480, QTcB/F > 450)
11	Exclusion #15 – Positive HIV antibody test
12	Any other deviations from inclusion/exclusion criteria which could impact the efficacy assessment.
13	Experience an exacerbation, which needed treatment with steroids during the treatment phase of the study
14	Not completing the Day 80 PROactive endpoint, Week 13 (Day 90) lean mass and all of the functional assessments (leg press strength, peak performance from Incremental shuttle walking test, Constant Work Rate (CWR) duration from endurance shuttle walking test, total SPPB score and handgrip strength).
15	Permanent discontinuation of the treatment during the study treatment period (This check must will be performed by Statistics and Programming).

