**ECG Parameters**

**General**

- The summary should be based on average value of triplicate ECG readings obtained over a brief recording period (missing readings will not be counted).

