**Eligibility Criteria**

- The QT values at screening will be using for the eligibility checking of subjects.

ECG Parameters
Stopping Criteria

A subject who meet either of the bulleted criteria below will be withdrawn from the study:
 
 
• QT interval corrected for heart rate by Bazett's formula (QTcB) or QT interval corrected for heart rate by Fridericia's formula (QTcF) >450 msec
 
• QT interval corrected for heart rate (QTc) >480 msec in participants with Bundle Branch Block based on a single ECG.
 

Laboratory Parameters
General

 
• All clinical laboratory tests will be based on central laboratory assessments only. If a laboratory value which is expected to have a numeric value for summary purposes, has a non-detectable level reported in the database, where the numeric value is missing, but typically a character value starting with '<x' or '>x' (or indicated as less than x or greater than x in the comment field) is present, the number of significant digits in the observed values will be used to determine how much to add or subtract in order to impute the corresponding numeric value.             
 
○ Example 1: 2 Significant Digits = '< x' becomes x - 0.01
 
○ Example 2: 1 Significant Digits = '> x' becomes x + 0.1
 
○ Example 3: 0 Significant Digits = '< x' becomes x - 1
 
 
 

Laboratory Toxicity Grade															

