**12.8.2. ECG**

ECG Parameter	Units	Clinical Concern Range	
		Lower	Upper
Absolute			
Absolute QTc Interval	msec	N/A	> 500
Uncorrected QT	msec	N/A	> 600
Change from Baseline			
Increase from Baseline QTc	msec	N/A	> 60

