3.14.	Safety	AE3	Summary of Adverse Events of Special Interest	IDSL – To display by page for CV events and Liver events	Headline Results & SAC
Laboratory: Chemistry					
3.15.	Safety	LB1	Summary of Chemistry Changes from Baseline by Visit	ICH E3	SAC
3.16.	Safety	LB16	Summary of Chemistry Results by Maximum Grade Increases Post-baseline Relative to Baseline	ICH E3	SAC
3.17.	Safety	LB4	Summary of Chemistry Shifts from Baseline Relative to Normal Range	IDSL	SAC
Laboratory: Haematology					
3.18.	Safety	LB1	Summary of Haematology Changes from Baseline	ICH E3	SAC
3.19.	Safety	LB16	Summary of Haematology Results by Maximum Grade Increases Post-baseline Relative to Baseline	ICH E3	SAC
3.20.	Safety	LB4	Summary of Haematology Shifts from Baseline Relative to Normal Range	IDSL	SAC
Laboratory: Urinalysis					
3.21.	Safety	LB1	Summary of Urine Concentration Changes from Baseline	ICH E3	SAC

Safety: Tables					
No.	Population	IDSL / Example Shell	Title	Programming Notes	Deliverable [Priority]
3.22.	Safety	UR1	Summary of Worst Case Urinalysis Results (Discrete or Character Values) Post-Baseline Relative to Baseline	ICH E3 Including glucose, protein, blood	SAC
3.23.	Safety	LB4	Summary of Urinalysis Shifts from Baseline Relative to Normal Range	IDSL	SAC
Laboratory: Hepatobiliary (Liver)					
3.24.	Safety	LIVER10	Summary of Hepatobiliary Laboratory Abnormalities	IDSL	SAC
Laboratory: Other					
3.25.	Safety	LB1	Summary of Sex/Reproductive Hormones	Summarize Testosterone, Free Testosterone, Sex hormone-binding globulin (SHBG), Follicle-stimulating hormone (FSH), Luteinizing hormone (LH) and Prostate specific antigen (PSA).	SAC
3.26.	Safety	LB1	Summary of Lipid Panel		SAC
3.27.	Safety	LB1	Summary of hsCRP, Fibrinogen		SAC
ECG					
3.28.	Safety	EG1	Summary of ECG Findings	IDSL	SAC
3.29.	Safety	EG10	Summary of Maximum QTc Values Post-Baseline Relative to Baseline by Category	IDSL	SAC
3.30.	Safety	EG2	Summary of Change from Baseline in ECG Values by Visit	IDSL	SAC
3.31.	Safety	EG11	Summary of Maximum Increase in QTc Values Post-Baseline Relative to Baseline by Category	IDSL	SAC
Vital Signs					

Safety: Tables					
No.	Population	IDSL / Example Shell	Title	Programming Notes	Deliverable [Priority]
3.32.	Safety	VS1	Summary of Change from Baseline in Vital Signs	ICH E3	SAC

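### SAP 12.6.3 states the entry QTc cut-offs as withdrawal criteria, and SAP 12.7.2.1 gives every adverse event with a known post-treatment onset and a missing stop day a duration of 0 or less

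*SAP*

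**What the plan says.** **QTc.** SAP 12.6.3, ECG Parameters, has a short eligibility entry (screening QT values are used) followed by a stopping entry that opens "A subject who meet either of the bulleted criteria below will be withdrawn from the study". Its two bullets are QTcB or QTcF above 450 msec, and QTc above 480 msec with BBB on one ECG. Protocol 6.2, exclusion 14, sets the same limits for entry; its BBB part reads "QTc) >480 msec in participants with Bundle Branch Block based on a single ECG". SAP 12.1.1, item 10, also treats them as entry limits: "ECG values above ranges (QTc > 480, QTcB/F > 450".

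Protocol 8.1.2 bases withdrawal on averaged triplicate ECGs, at "QTc >500 msec OR Uncorrected QT >600 msec" or "Increase from baseline of QTc >60 msec". With BBB the limits are >500 msec (baseline <450) or ≥530 msec (baseline 450 to 480). SAP 12.8.2 lists 500 and 600 msec as absolute limits and 60 msec for "Increase from Baseline QTc". The general ECG entry of SAP 12.6.3 says "The summary should be based on average value of triplicate ECG readings".

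**AE dates.** SAP 12.7.2.1 covers AE dates recorded without the day of the month and applies to time to onset and duration. A missing stop day becomes the end of the month, but if that falls after treatment stop, the treatment stop date is used. Fully missing dates stay missing. SAP 12.6.3 defines duration as resolution minus onset plus 1. Protocol 9.3.1 collects AEs up to the follow-up visit, which Protocol 5.1 places 42 ± 7 days after the last dose. SAP 8.1 and 12.4.1 show AEs regardless of treatment phase.

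**The concern.** Safety, including ECGs and AEs, is a primary objective, so the rules behind those data should be right.

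On QTc, a stopping lead-in has been joined to eligibility bullets. Taken literally, a participant without BBB who entered at the permitted maximum of 450 msec would qualify for withdrawal after a rise of 1 msec, on one ECG. The SAP then disagrees with the protocol and with its own 12.8.2, and a programmer asked to flag stopping events would find two different sets of limits.

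On AE dates, the cap ignores the fact that AEs can begin after dosing ends. An event in the six-week follow-up period with a missing stop day would be given a stop date before its start. The start-day rule has a floor at treatment start, but the stop-day rule has no check against onset.

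**Working it through.** **QTc: the texts side by side (msec)**

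| | SAP 12.6.3 stopping | Protocol 6.2, excl. 14 (entry) | Protocol 8.1.2 stopping | SAP 12.8.2 |
|---|---|---|---|---|
| QTc, no BBB | >450 | >450 | >500 | >500 |
| QTc, BBB, baseline <450 | >480 | >480 | >500 | no separate limit |
| QTc, BBB, baseline 450–480 | >480 | >480 | ≥530 | no separate limit |
| Uncorrected QT | none | none | >600 | >600 |
| Rise from baseline | none | none | >60 | >60 |
| Basis for BBB limit | single ECG | single ECG | mean of triplicate | summaries use mean of triplicate (12.6.3) |

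The SAP stopping text matches the entry column, not the stopping column. The gaps are 500 − 450 = 50 msec without BBB; with BBB, 500 − 480 = 20 msec (baseline <450) or 530 − 480 = 50 msec (baseline 450 to 480).

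The SAP text is not simply a stricter rule, because the disagreement runs both ways. Without BBB:
- QTc 460 from baseline 440 is a rise of 20. It exceeds 450 but neither 500 nor the 60 msec rise, so only the SAP text is met.
- QTc 445 from baseline 380 is a rise of 65. It exceeds the 60 msec rise but not 450, so only the protocol is met.

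**AE duration**

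Let T be the treatment stop date and O = T + k a known onset, with k ≥ 1. The stop month is the onset month or later, so its last day is on or after O and hence after T. The cap therefore always applies, and the imputed stop is T:

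duration = T − (T + k) + 1 = 1 − k ≤ 0.

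- k = 1 gives 0; k = 42 gives −41.
- Follow-up at 42 ± 7 days means a visit 35 to 49 days after the last dose. An onset on the visit day gives 1 − 35 = −34 to 1 − 49 = −48.
- Example: last dose 31 March, onset 10 April, stop recorded as April. Here k = 10, so the duration is −9 days. Month-end gives 30 − 10 + 1 = 21 days.

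Calendar enumeration confirms the identity. Over 365 last-dose dates, onsets 1 to 42 days later and true lengths of 1 to 14 days ending by a day-42 visit, the SAP rule gives 0 or less in 181,405 of 181,405 combinations. Month-end capped at the visit gives 0 or less in none, with an error of 0 to +30 days. These counts are date combinations, not expected AEs.

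**Onset on or before treatment stop**

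Here the duration is always at least 1 and the cap can help or harm.
- Onset 5 April, last dose 10 April, true end 20 April (16 days): the cap gives 6 and month-end gives 26, an error of 10 days either way.
- Same dates, true end 8 April (4 days): the cap gives 6 (error 2) and month-end gives 26 (error 22).

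For on-treatment onsets 0 to 30 days before the last dose that resolve 1 to 42 days after it, the cap is short in all 475,230 enumerated combinations, by 1 to 42 days. For the same onsets with length 1 to 14 days that resolve by the last dose, uncapped month-end (limited only by a day-42 visit) is worse in 71,365 combinations, equal in 53,830 and better in none.

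**The case against.** The best defence is that neither slip reaches a result. Sites withdraw participants under Protocol 8.1.2; the SAP describes analyses for the study report. The planned ECG outputs, Tables 3.28 to 3.31 (for example "Summary of Maximum QTc Values Post-Baseline Relative to Baseline by Category") and Listings 30 to 32, name no stopping flag, and SAP 12.8.2 has the right limits for clinically important values. SAP Table 1 records no change to the stopping rule, but it covers statistical analyses, so its silence says little. All of this stands. A reader might infer that participants were withdrawn wrongly or that QTc results will be misreported. The documents do not support either.

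For AE dates, the impossible value needs a known onset after dosing and a stop date lacking only the day. AE counts and incidence do not change, listings show the partial date as captured, and no planned table is titled by duration. Whether a standard listing prints derived duration depends on shells outside these documents. This also stands, and it limits the consequence without making the rule correct. The concomitant-medication rule in the same section uses month-end without this cap, but those dates serve phase assignment, so it is not a contradiction.

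Two further readings go too far. One is that the cap should be removed altogether. For on-treatment onsets that is a trade-off, as the last check shows. The other is a floor of −54 days, taken from the visit windows alone (day 85 to day 140, 55 days). Protocol 5.1 limits follow-up to 49 days after the last dose.

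**Conclusion.** Both errors are in the text and both are minor.

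The SAP 12.6.3 stopping text is wrong by 50 msec without BBB and by 20 or 50 msec with it. It also omits the uncorrected-QT and rise-from-baseline limits and ties its BBB limit to a single ECG. It contradicts the protocol and SAP 12.8.2. No effect on a participant or a planned output is shown. The 450 msec bullet is read here as applying without BBB, as in exclusion 14.

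The SAP 12.7.2.1 cap gives a duration of 1 − k, never above 0, for every AE with a known onset k days after treatment stop and a missing stop day. The lower limit of −34 to −48 days assumes follow-up within 42 ± 7 days of the last dose. Only derived durations are affected; AE counts, incidence and efficacy are not. The documents do not say how many stop dates will be partial, and the number could be zero.

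**What to change.** **QTc.** Replace the stopping text in SAP 12.6.3 with the Protocol 8.1.2 criteria: mean of triplicate ECGs; QTc >500 msec, uncorrected QT >600 msec, or a rise from baseline >60 msec; with BBB, >500 msec if baseline is <450 and ≥530 msec if baseline is 450 to 480. Move the 450/480 text to the eligibility entry.

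**AE dates.** In SAP 12.7.2.1, apply the treatment-stop cap only when onset is on or before treatment stop. For later onsets, impute month-end, capped at last study contact (follow-up visit, study exit or death) and never earlier than onset. Every such duration is then at least 1 day. Leave the rule for on-treatment onsets as it is unless the team wants to revisit that trade-off.

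**Cost.** Two wording corrections and one condition in the AE date derivation, with no new data. Month-end can overstate duration by up to 30 days. For example, last dose 29 May, onset 30 May, true length 5 days and stop recorded as June gives 32 days, an error of 27. The gain is the removal of impossible values, not a more accurate duration for each event.

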## 12.7. Appendix 7: Reporting Standards for Missing Data

### 12.7.1. Premature Withdrawals

Element	Reporting Detail
General	
 
• Subject study completion (i.e. as specified in the protocol) was defined as subjects who completed all visits of the study including the follow-up visit.
 
• Withdrawn subjects may be replaced in the study.
 
• All available data from participants who were withdrawn from the study will be listed and all available planned data will be included in summary tables and figures, unless otherwise specified.
 
• Withdrawal visits will be assigned to a planned visit or an unscheduled visit and will be slotted as per Appendix 3: Assessment Windows.
 

### 12.7.2. Handling of Missing Data

Element	Reporting Detail
General	
 
• Missing data occurs when any requested data is not provided, leading to blank fields on the collection instrument: 
 
○ These data will be indicated by the use of a “blank” in subject listing displays. Unless all data for a specific visit are missing in which case the data is excluded from the table.
 
○ Answers such as “Not applicable” and “Not evaluable” are not considered to be missing data and should be displayed as such.
 
 
 

Outliers	
 
• Any participants excluded from the summaries and/or statistical analyses will be documented along with the reason for exclusion in the clinical study report.
 

#### 12.7.2.1. Handling of Missing and Partial Dates

Element	Reporting Detail
General	
 
• Partial dates will be displayed as captured in subject listing displays.
 

Adverse Events	
 
• The eCRF allows for the possibility of partial dates (i.e., only month and year) to be recorded for AE start and end dates; that is, the day of the month may be missing. In such a case, the following conventions will be applied for calculating the time to onset and the duration of the event: 
 
○ Missing Start Day: First of the month will be used unless this is before the start date of study treatment; in this case the study treatment start date will be used.
 
○ Missing Stop Day: Last day of the month will be used, unless this is after the stop date of study treatment; in this case the study treatment stop date will be used.
 
 
 
• Completely missing start or end dates will remain missing, with no imputation applied. Consequently, time to onset and duration of such events will be missing.
 

Concomitant Medications/ Medical History	
 
• Partial dates for any concomitant medications recorded in the CRF will be imputed using the following convention: 
 
○ If the partial date is a start date, a '01' will be used for the day and 'Jan' will be used for the month
 
○ If the partial date is a stop date, a '28/29/30/31' will be used for the day (dependent on the month and year) and 'Dec' will be used for the month.
 
 
 
• The recorded partial date will be displayed in listings.
 

## 12.8. Appendix 8: Values of Potential Clinical Importance

### 12.8.1. Laboratory Values

Haematology				
Laboratory Parameter	Units	Category	Clinical Concern Range	
			Low Flag (< x)	High Flag (>x)
Hematocrit	Ratio of 1	Male		0.54
		Female		0.54
		Δ from BL (Female & Male)	0.075	
Haemoglobin	g/L	Male		180
		Female		180
		Δ from BL (Female & Male)	25	
Lymphocytes	x10  /L		0.8	
Neutrophil Count	x10  /L		1.5	
Platelet Count	x10  /L		100	550
White Blood Count (WBC)	x10  /L		3	20

Clinical Chemistry				
Laboratory Parameter	Units	Category	Clinical Concern Range	
			Low Flag (< x)	High Flag (>x)
Albumin	g/L		30	
Calcium	mmol/L		2	2.75
Creatinine	μmol/L	Δ from BL		44.2
Glucose	mmol/L		3	9
Phosphorus	mmol/L		0.8	1.6
Potassium	mmol/L		3	5.5
Sodium	mmol/L		130	150
Total CO 2 (Bicarbonate)	mmol/L		18	32

Liver Function				
Test Analyte	Units	Category	Clinical Concern Range	
ALT/SGPT	U/L	High	>=3xULN	
AST/SGOT	U/L	High	>=2xULN	
Alkaline phosphatase	U/L	High	>=2xULN	
T Bilirubin	μmol/L	High	>=1.5ULN	
T. Bilirubin + ALT	μmol/L U/L	High	>=1.5ULN T. Bilirubin + >=3xULN ALT	

**12.8.2. ECG**

ECG Parameter	Units	Clinical Concern Range	
		Lower	Upper
Absolute			
Absolute QTc Interval	msec	N/A	> 500
Uncorrected QT	msec	N/A	> 600
Change from Baseline			
Increase from Baseline QTc	msec	N/A	> 60

**12.8.3. Vital Signs**

Vital Sign Parameter (Absolute)	Units	Clinical Concern Range	
		Lower	Upper
Systolic Blood Pressure	mmHg	<85	>160
Diastolic Blood Pressure	mmHg	<45	>100
Pulse Rate	Beats/min	<40	>110
Respiratory Rate	breaths/min	N/A	>20
Temperature (skin)	°C	N/A	>38

**12.9. Appendix 9: Model Checking and Diagnostics for Statistical Analyses**

Analysis	Mixed Model Repeated Measure (MMRM)

 
Distributional assumptions underlying the model used for analysis will be examined by obtaining a normal probability plot of the residuals and a plot of the residuals versus the fitted values (i.e. checking the normality assumption and constant variance assumption of the model respectively) to gain confidence that the model assumptions are reasonable.
 
	
Analysis	Bayesian Analysis

 
Non-informative prior should be plotted to make sure it is truly non-informative.
 
Adequate values for the number of MCMC samples / thinning / number of burn-in samples should be chosen to ensure that the ratio Monte Carlo Standard Errors (MCSE) and standard deviation of the posterior distribution for all the parameters in the model as small as possible, typically close to 0.01.
 
In addition, if possible, the number of tuning units and maximum number of tuning iterations may be increased to find a better proposal distribution for the model parameters, which in turn may reduce the MCSE/SD ratio.
 
The Geweke diagnostic test checks whether the mean estimates have converged by comparing means from the early and latter part of the Markov chain using a z score t-test. Large absolute values of the z-score statistic indicate rejection of the null hypothesis of no difference between the mean estimates obtained from the early and latter parts of the chain.
 
The convergence diagnostics for all parameters in the Bayesian analysis will be visually checked by the trace plots.
 
If the trace plots show apparent trend or the autocorrelation plots show significant positive or negative autocorrelation, number of iterations will be increased or reparameterization might be explored.
 
	
Analysis	Analysis of covariance (ANCOVA)

 
Distributional assumptions underlying the model used for analysis will be examined by obtaining a normal probability plot of the residuals and a plot of the residuals versus the fitted values (i.e. checking the normality assumption and constant variance assumption of the model respectively) to gain confidence that the model assumptions are reasonable.
 
	

